4.1.2.1 Women of Childbearing Potential (WOCBP)

For the purposes of this study, women of childbearing potential are defined as all women who are capable of becoming pregnant, unless they meet one of the following criteria:

- 1. 12-months post-menopausal
- 2. Post-hysterectomy
- 3. Surgically sterile

If a female subject does not meet these criteria and is considered of childbearing potential, they will be excluded from the clinical trial.

4.2 Recruitment

Approximately 60 subjects will be screened, and after screening, approximately 40 subjects are expected to complete the study. All subjects will be given the option to participate in the optional repeat LP sub-study and the optional MRI sub-study until 12 subjects have completed each sub-study. Subjects will be given the choice to complete either the repeat LP sub-study, the MRI sub-study, or both.

4.2.1 Recruitment of Subjects through Advertising

Advertisement flyers will be posted on bulletin boards around MGB campuses (both the main campus and Charlestown campus) to advertise for the study as well posting as an advertisement on Partners Rally for Research. A phone number will be provided that will ring directly to the research coordinator, and voice messages can be left for the coordinator on a password-protected voice mailbox. The study coordinator will contact the subject and explain study in further detail and if the subject is interested, potentially complete a telephone prescreening. A listing of the study will also be posted on the MGH ACTRU website as well the websites of our affiliates.

A Crossover, Randomized Block Sequence, Double-Blind, Placebo-Controlled Trial for Nicotinamide Riboside in Subjective Cognitive Decline and Mild Cognitive Impairment in Aging

Version:4.4

Subjects may also be recruited through the distribution of IRB approved recruitment materials at community outreach initiatives including informational sessions to various community partners such as city-based and non-profit organizations.

4.2.2 Recruitment of Subjects from among the Investigator's own Patients and MGB Providers

Subjects will also be recruited from the outpatient clinical practices of the principal investigator ([name]). If the potential subject is the investigator's patient, another member of the study or clinic staff will introduce the study to the patient and determine if they are interested in learning more about the study. An NP investigator will be made available to explain the study to the subject at their request. If the potential subject is not the investigator's patient, the investigators will not directly approach the patient regarding possible participation in the study. Other MDU physicians (not participating directly in the study) may discuss the study directly with their patients, if they choose to do so. The prospective participant will be given informational papers to review and the study coordinator will contact them to discuss interests and research opportunities.

Subjects will also be recruited from physician specialists at the Center for Alzheimer Research and Treatment (CART) at Brigham and Women's Hospital, a database of patients who have indicated a prior interest in participating in studies at the CART, the memory disorders, neurology, psychiatry, and medicine clinics at Brigham and Women's Hospital and Massachusetts General Hospital, and physicians outside of the Partners network.

Other providers across MGB will also be made aware of the study (including key eligibility criteria) via email and provided a link to the Rally ad. These providers (not participating directly in the study) may discuss the study directly with their patients, if they choose to do so. If the prospective patient is interested, their provider will give them a copy of the consent form (unstamped) for review as well as a link to the Rally ad, which contains the research coordinator's contact information.

4.2.3 Recruitment of Subjects from the Massachusetts Alzheimer's Disease Research Center

Subjects will also be recruited from an observational study that follows a longitudinal research cohort (LC) of approximately 400 active research participants in the Massachusetts Alzheimer's Disease Research Center (MADRC) recruited from the MGH's Memory Disorders Unit clinic and other diverse sources. LC subjects are followed-up on an approximately annual basis, either in-person at the MGH or by means of a telephone follow-up 'visit'. Study staff will only contact subjects that have indicated to the MADRC that they are interested in hearing about/participating in other studies. MADRC may also share information regarding our studies with their mailing list.

4.2.4 Recruitment of Subjects from Providers Outside of MGB

Subjects will be recruited from providers outside of MGB through the use of doctor to doctor letters and/or sharing of IRB-approved recruitment materials. Appropriate providers who have been identified by the study team will be mailed IRB approved materials that introduce the study and outline the specific inclusion/exclusion criteria. Providers will be asked to identify eligible participants and share their information with us following all local policies on patient privacy including, but not limited to, obtaining written consent as needed.

4.2.5 Recruitment from the CTRU Registry

A research volunteer registry (P2021000916) was established in 2021 to maintain a list of people interested in participating in clinical research with the MGH Clinical and Translational Research Unit (CTRU). The goal of the CTRU, located in CNY 149, is to serve the clinical and research departments, institutes, centers, programs

A Crossover, Randomized Block Sequence, Double-Blind, Placebo-Controlled Trial for Nicotinamide Riboside in Subjective Cognitive Decline and Mild Cognitive Impairment in Aging

Version:4.4

and labs that comprise the MGH Neuroscience community and to be a foundational component and research core facility within MGH's emerging translational programs. Eligible participants who have consented to be contacted for future research may be identified using data stored within the volunteer registry.

4.2.6 Recruitment from the MAINAH Registry

The Northern Light Health site will be recruiting from their internal research registry, the Maine Initiative for Neurologic Aging and Health (MAINAH). With over 800 enrollees and growing, including people from all over Maine, of all ages, many of whom either have family members with dementia or themselves have some cognitive symptoms. All enrollees have communicated interest in participating in research. MAINAH registry participants will be contacted using an IRB-approved email to let them know about this opportunity.

5. SUBJECT ENROLLMENT

5.1 Informed Consent Process

This study will be conducted in compliance with Title 21 Part 50 of the United States of America Code of Federal Regulations (CFR), Federal Regulations, and ICH Guidance Documents pertaining to informed consent.

Potential subjects will be given general information about the research (e.g., through informational sheets, letters, or discussion with their treating physicians). If they are interested in learning more about the study, they will then contact the research coordinator. The research coordinator will obtain verbal consent in accordance with Partner's Prescreening Guidelines prior to performing a telephone prescreening interview. If the subject meets prescreening criteria, including scoring a 27 or greater on the Telephone Interview for Cognitive Status or scoring a 3 or greater on the Cognitive Functioning Instrument, and wishes to continue the screening process, a virtual, Zoom videoconference screening visit will be scheduled. If the subject resides outside the state of Massachusetts, the screening visit will take place in person at MGH CNY campus.

At the screening visit, the investigator will meet with the potential subject to review and discuss the details of the study using the informed consent document as a guide. A copy of the informed consent document will be sent to the subject before the screening visit takes place, and they will have at least 24 hours between when the document is received and when the screening visit is scheduled in order for the subject to have adequate time to fully review the Informed Consent Document.

The informed consent process will be conducted using a REDCap-based electronic consent form. The consent form has been developed in REDCap, a secure, web-based, HIPAA-compliant, data collection platform with a user management system allowing project owners to grant and control varying levels of access to data collection instruments and data for other users. If requested by the subject, a traditional hard copy consent form will be provided to the subject along with any materials needed for return shipping.

During the screening visit, the informed consent document will be reviewed with the participant by an experienced clinician investigator. The potential subject may ask to speak with the physician investigator should a non-physician investigator be involved in obtaining informed consent. The informed consent discussion will include all of the required elements of informed consent, including the purpose of the research, the procedures

A Crossover, Randomized Block Sequence, Double-Blind, Placebo-Controlled Trial for Nicotinamide Riboside in Subjective Cognitive Decline and Mild Cognitive Impairment in Aging

Version:4.4

to be followed, the risks and discomforts, as well as potential benefits associated with participation, and alternative procedures to study participation. Their questions will be answered to their satisfaction. The subject will be provided with adequate time to reflect on the potential benefits and risks and possible discomforts of participation, and to make an informed decision.

After reviewing the consent form in full, the informed consent worksheet will be administered verbally to the participant by an experienced clinician investigator. The subject must get 70% of questions 1-10 correct, and 100% on questions 11-14. If the subject does not get 70% of questions 1-10 correct and 100% on questions 11-14 on the first attempt, the investigator will review the details of the study again with the subject. The subject will then be given another opportunity to answer the consent worksheet questions. If the subject does not answer 70% of questions 1-10 correct and 100% on questions 11-14 on the second try, they will be considered unable to consent and therefore ineligible for the study.

If the participant is deemed capable of consenting, a link will be sent to the REDCap e-consent form or the subject will sign the provided hard-copy informed consent form. For REDCap e-consent, participant signatures will be obtained using electronic signature via mouse followed by electronic signature by the experienced clinician investigator. Signed hard-copy consent forms will be mailed back or given to the study team and signed by the consenting investigator upon receipt. Upon completion of the informed consent process, participants will be provided with an electronic copy of the signed consent form and hard copies will be stored in each subject's binder. If a participant prefers a hard copy of the consent form, it will be given to them at their Lead-In in person visit.

While some subjects will have MCI, they must be deemed capable of providing informed consent by the Investigators. Subjects who are not capable of providing informed consent will be excluded from this study.

5.2 Remuneration

Subjects will receive \$25 for their participation in each Visit. Subjects will receive \$100 for the first optional LP they undergo, and \$75 for each additional optional LP they elect to receive. If subjects elect to undergo all three LPs, they will receive a \$50 LP sub-study completion bonus. If subjects elect to participate in MRIs, they will receive \$75 for the first MRI, \$100 for the second MRI, and \$150 for the third MRI. Subjects will also receive \$100 upon completion of the overall study as long as they were at least 80% compliant with all at-home study activities, including medication dosing, brain games, and Fitbit activity tracking. Therefore, if a subject elects to undergo all additional procedures and are at least 80% compliant with at-home study tasks, the maximum amount a subject would be eligible to receive is \$925 at study completion. If a subject does not elect to participate in any optional procedures but is compliant with study tasks, they would be eligible to receive \$300. We anticipate some subjects may come from outside the region and if so, appropriate travel expenses may be reimbursed including transportation up to \$150. To minimize the inconvenience of frequent visits, meal and parking vouchers for use at the MGH Charlestown Navy Yard (CNY) facilities will also be offered at each visit.

5.3 Randomization

A Crossover, Randomized Block Sequence, Double-Blind, Placebo-Controlled Trial for Nicotinamide Riboside in Subjective Cognitive Decline and Mild Cognitive Impairment in Aging

Version:4.4

Subjects will be randomized into one of two counter-balanced block sequences (see Figure 4 below). Randomization will be done by MGH Clinical Trials Pharmacy.

[figure not shown]

Figure 4. Study Schema

5.4 Reasons for Withdrawal

A study subject will be discontinued from participation in the study if:

- Any clinical adverse event (AE), concurrent illness, or other medical condition or situation occurs such that continued participation in the study would not be in the best interest of the subject.
- The subject meets any exclusion criteria (either newly developed or not previously recognized).
- The subject is less than 80% or greater than 120% compliant with NR dosing.

Subjects are free to withdraw from participation in the study at any time upon request.

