7.1.3.2 Cognitive Exercises

Each subject will be provided with a Lumosity (Lumos, Labs, Inc.) account. The subjects will be required to complete 6 different cognitive exercises (about 10-15 minutes) at least 6 days per week for the duration of the study (from Days 0 to 140). The assigned cognitive exercises will sample the domains of attention, processing speed, memory, cognitive flexibility, and problem solving. Compliance can be assessed by the study coordinator by logging on to each subject's Lumosity account. If the subject is not adhering to the cognitive exercise requirements, the study coordinator will contact the subject to remind them of proper exercise procedures. If a subject requires more than three such reminders, they will be considered non-compliant, and PI will determine if the subject should continue in the study or if their study participation should be discontinued.

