8.3 Dosage, Preparation and Administration of Study Intervention

Niagen NR 500 mg (two capsules) or PBO (two capsules) should be taken orally twice daily with food. The capsules should be swallowed whole.

A Crossover, Randomized Block Sequence, Double-Blind, Placebo-Controlled Trial for Nicotinamide Riboside in Subjective Cognitive Decline and Mild Cognitive Impairment in Aging

Version:4.4

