8.4 Modification of Study Intervention for a Subject

Dosing may be reduced or suspended at any time by the PI or designated licensed clinician sub-investigator. This will be documented along with the reason(s) and dates of adjustment in the CRF for each subject requiring this manipulation. The PI or designated licensed clinician Sub-Investigator may reduce or suspend the dosage of study dietary supplement or discontinue the study supplement for AEs thought to be related to the study supplement or for other reasons during the trial (the reason and dates of reduction or suspension or dose reduction or suspension must be documented in CRF). If the AE is mild or moderate, the dosage may be restarted after the event improves. If the AE is serious or life threatening and deemed to be definitely related to the dietary supplement, the study dietary supplement will be discontinued immediately. Study subjects must remain off the study dietary supplement permanently. Subjects may not resume study dietary supplement. All AEs will be followed to resolution.

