8.5 Assessment of Subject Compliance

Subjects will be instructed to return empty and unused study dietary supplement containers at each clinic visit or the Early Discontinuation Visit. Research staff will review returned and unused study dietary supplement and log information into the reconciliation form to determine compliance. Non-compliance will be defined as taking less than 80% or more than 120% of study agent as determined by unused capsule counts. If a study subject is non-compliant with study dietary supplement, research staff should re-educate and train the subject in administration of study agent. If the subject's non-compliance persists, it will be left up to the PI to determine whether the subject should be discontinued from the study.

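### Section 5.4 makes removal mandatory outside 80–120% compliance while 8.5 leaves it to the PI; followed as written, 5.4 costs RBANS scores that the intention-to-treat analysis needs

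*Combined protocol and SAP*

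**What the plan says.** Section 5.4 opens in mandatory terms: a subject meeting any listed condition is taken out of the study, not only off the capsules. One condition is "The subject is less than 80% or greater than 120% compliant with NR dosing". It gives no re-education step and no discretion.

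Section 8.5 sets the same limits for a differently named quantity: "Non-compliance will be defined as taking less than 80% or more than 120% of study agent as determined by unused capsule counts". Staff are to retrain the subject and, if the problem persists, "it will be left up to the PI to determine whether the subject should be discontinued from the study".

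Other sections bear on the same event:

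- 8.4 allows clinicians to change the dose: "Dosing may be reduced or suspended at any time by the PI or designated licensed clinician sub-investigator". It adds: "If the AE is mild or moderate, the dosage may be restarted after the event improves".
- 7.1.3.2 handles missed brain games by reminders, after which the "PI will determine if the subject should continue in the study or if their study participation should be discontinued". Section 7.1.3.3.1 does the same for the activity tracker.
- 11.3.1 leaves removal to the investigators and names no capsule threshold.
- 8.4.1 implies that a subject may stop the supplement and stay in the study, but no section lists that subject's visits.
- 9.1 commits to an intention-to-treat primary analysis of all randomised subjects on RBANS Total at Days 28, 84 and 140. It uses a matched-pair t-test and a mixed model. It does not say how a missing RBANS or an Early Termination RBANS is handled.

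**The concern.** One event, a capsule count outside the limits, carries two incompatible instructions. A coordinator who finds 75% at Day 84 must either remove the subject (5.4) or retrain and refer to the PI (8.5). Either choice departs from the protocol, and 6.1.7 counts any departure as a deviation. The wording differs too. Read literally, 5.4 covers only the NR period, which blinded staff cannot identify, whereas 8.5 covers the study agent in both periods.

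The statistical stake is what happens after removal. Adherence is a post-randomisation variable that may be related to tolerability, motivation or cognition. Ending follow-up because of it makes RBANS data missing for a reason that may be related to outcome. An intention-to-treat analysis is meant to avoid this by following subjects whether or not they take the capsules.

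**Working it through.** The plan states no power, target effect, within-subject SD or dropout rate, so there is no figure of its own to reproduce. The check is of the text, followed by two short calculations.

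**Which scores are lost.** Under 6.1.3 the RBANS is done by video up to 4 days before the office visit, and 8.5 has containers returned at clinic visits. Mid-block contacts (6.1.4) are by telephone, so removal on a capsule count is most likely at Day 84 or Day 140.

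- Failure found at Day 140: that RBANS has already been done, so nothing is lost.
- Failure found at Day 84: Days 28 and 84 are in hand and Day 140 is lost. The subject has a score from only one randomised block, so there is no NR–placebo difference for the matched-pair t-test. The mixed model keeps the earlier scores, but its estimate is then valid only under missing-at-random.
- Early Termination visit: 6.1.6 includes cognitive testing, and the schedule's footnote 8 names RBANS. It is by invitation and within 7 days of stopping treatment. After removal at Day 84 it would therefore be a second reading after the first block, not a reading under the second treatment.

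**Can a pause allowed by 8.4 trip the limit?** The dose comes from 8.3: "Niagen NR 500 mg (two capsules) or PBO (two capsules) should be taken orally twice daily with food". Block length is 8 weeks (3.1).

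- Capsules per block: 2 × 2 × 56 = 224. The 80% line is 0.80 × 224 = 179.2.
- 11 days off: (56 − 11) × 4 = 180; 180/224 = 80.4%, inside.
- 12 days off: (56 − 12) × 4 = 176; 176/224 = 78.6%, outside.
- Half dose for 22 days: 22 × 2 + 34 × 4 = 180, or 80.4%, inside. For 23 days: 23 × 2 + 33 × 4 = 178; 178/224 = 79.5%, outside.

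These percentages assume that compliance is counted against the full scheduled dose. If the denominator is the dose prescribed after the clinician's change, an ordered pause costs nothing. The protocol does not say which applies.

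**Precision.** With a fraction L of pairs lost from N = 40, the paired standard error is multiplied by √(N/[N(1 − L)]) = 1/√(1 − L). The within-subject SD cancels. The values of L are assumptions.

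| L | Pairs left | SE ratio |
|---|---|---|
| 10% | 36 | 1/√0.9 = 1.054 |
| 20% | 32 | 1/√0.8 = 1.118 |
| 30% | 28 | 1/√0.7 = 1.195 |

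**Bias.** Let d be the amount by which the mean NR–placebo difference in removed subjects falls below that in completers. The all-randomised mean is (1 − L)C + L(C − d) = C − Ld, where C is the completers' mean. The completer estimate is therefore too high by L × d, or 0.1 to 0.3 RBANS points for each point of d when L is 10–30%. The documents give neither L nor d, so the size of any bias is unknown.

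**The case against.** The best defence is that 5.4 is an outlier that staff may never apply. Section 8.5 is the specific procedure; the game and tracker rules and 11.3.1 all leave the decision to investigators. Section 5.2 pays a completion sum "as long as they were at least 80% compliant with all at-home study activities, including medication dosing", which suggests that subjects below 80% might still finish, though this is weak evidence because the condition also covers games and the tracker. The defence stands as a forecast of practice. It does not remove the conflict, because the section that governs withdrawal uses mandatory words.

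A reader might infer four stronger things that the documents do not support:

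- That 5.4 ends all RBANS collection. It does not: Day 84 and Day 140 scores precede the office count, and an Early Termination RBANS is possible. Site-removed subjects may be covered by that visit, since 5.4 treats removal as withdrawal, although 5.4.1 speaks only of consent withdrawal.
- That 5.4 flatly contradicts 8.4. This depends on the undefined denominator.
- That NR side effects would make losses differ between sequences. Section 2.1.5 reports 2 dropouts for adverse events among 30 subjects in an earlier NR crossover, both on placebo, and 10.1.1 reports no event leading to NR discontinuation. Those were also not compliance removals.
- That the loss of precision can be stated in RBANS points or power from the SD of 9.1 and minimal detectable change of 5 in 9.1. The two come from different populations, and the confidence level behind the latter is not stated.

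It is also fair that this is an exploratory pilot with no claims attached. That bears on multiplicity and on how much weight the result carries. It does not excuse conflicting removal instructions.

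**Conclusion.** The conflict between 5.4 and 8.5 is direct and certain from the text. If 5.4 is followed, a first-block failure found at Day 84 costs the Day 140 RBANS, which weakens the stated intention-to-treat analysis without making it impossible. The clash with 8.4 is conditional: 12 days off in 56 breaches the limit only if ordered pauses count as missed doses.

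The size is modest on precision, a 5–20% larger paired standard error if 10–30% of pairs are lost. It is unknown on bias, which is the greater worry because removal would follow adherence. Both rest on assumed loss rates and on staff applying 5.4 rather than 8.5. The point is worth correcting, but it does not invalidate the design.

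**What to change.** - Replace the compliance bullet in 5.4 with the 8.5 rule (retrain, then PI decides), worded for the study agent rather than NR.
- State in 8.5 that compliance is counted against the dose prescribed after any reduction or suspension under 8.4.
- State in 5.4 and 8.4.1 that stopping capsules does not end follow-up. RBANS is still done at Days 84 and 140 unless the subject withdraws consent or the visit would be unsafe, and the scores are analysed as randomised.
- Offer the Early Termination visit explicitly to subjects removed by the investigator.

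The cost is a protocol amendment with the IRB approval that 3.3 requires. The visits are already scheduled. Following subjects who are off capsules may dilute the estimated effect, which is inherent in the intention-to-treat approach that the plan has chosen.
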